## **Background & Rationale**

Pulse oximeters are commonly utilized medical devices used to measure blood oxygen saturation (SpO2)[2]. These devices (such as the INNOVO Fingertip Pulse Oximeter) are either stand-alone or integrated into physiologic monitoring systems, using 2 wavelengths of lights to determine SpO2. With recent advances in technology, Spatial Frequency Domain Imaging (SFDI) using range of light wavelengths from red to near infrared (NIR) such as in Clarifi(R) (Modulated Imaging, Inc., Irvine CA), smartphones such as Apple Watch (Apple Inc., Cupertino, CA), transcutaneous oximetry TCOM (Perimed Inc., Las Vegas, NV) now have pulse oximetry capabilities. Since it is possible that most patients could utilize this technology, we sought to assess the accuracy, reliability and usability of these oximeters and compare outcomes. In this study, a cohort of 20 healthy volunteers above the age of 18 including males and females of different skin colors will be assessed at the same site and data will be compared. We aim to provide a set of data that will support the clinical and scientific community and identify more than one reliable skin oxygen measurement modalities. The Innovo pulse oximeter device will be used for all subjects.

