#### 1.0 **Objective(s)**

**1.1 Primary Objective** 

To investigate multiplatform for tissue oxygen measurement devices

**1.2** Secondary Objective

To compare other modalities with FDA approved Pulse Oximetry

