## **1.3 Tertiary/Exploratory/Correlative Objectives**

To investigate skin color biasness in the optical Oximeters. Fitzpatrick's skin type chart will be used to evaluate skin type.

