## 2.2 Secondary Outcome Measures

Comparison of the devices provides the standard for clinical use

2.3 Tertiary/Exploratory/Correlative Outcome Measures Melanin or scarred tissue oxygenation compared to normal skin

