## 4.0 Study Design

## 5.0 Enrollment/Randomization

Potential subjects will be identified from IU School of Medicine staff members. Each subject will use all four devices.

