## 6.0 Study Procedures

First the subjects will go through a questionnaire session about their medical history by a designated study team member. The questionnaire data will be placed in RedCap using a subject ID that cannot be linked back to the subject. Then the subject will be consented. Subject will be enrolled. Then the non-invasive data collecting procedure will start on the following equipment:

Spatial Frequency Domain Imaging (SFDI): During consenting period, the Modulim equipment will be calibrated and setup ready for scanning. Subject's volar aspect of the thumb along with the palm surface

will be ready to target the optical camera head. Actual scanning takes less than 60 seconds. The images will be processed offline. During processing 3-5 different regions of interest (ROI) will be taken to measure the oxygen parameters such as tissue oxygen saturation (StO2), oxy-hemoglobin (HbO2), deoxy-hemoglobin (HbR), superficial hemoglobin (HbT1, sub-surface hemoglobin (HbT2). The model used is a Clarifi Modulum

**Transcutaneous oxygen monitoring (TCOM)**: Transcutaneous oxygen monitoring (TCOM or TcpO2) is a noninvasive, clinically-approved method to obtain skin oxygen levels. The method is quantitative, and measures oxygen delivery to the skin from underlying tissue. Before positioning the electrode, an adhesive fixation ring will be placed on the dry skin on the volar aspect of the thumb and an electrolyte as a contact liquid will be filled half and the probe is aligned into it by rotating clock-wise to fasten it. Recording will be started and waited for the oxygen level to stabilize and a fixed value will be recorded. The model used is a Perimed PeriFlux 5000. The probe will be heated to about 45°C. Although this device has other options, only the measurement of  $O_2$  will be performed using this device.

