Statistical Analysis Plan

Protocol Title

Measurement of Oxygen Saturation in healthy human volunteers before, during and after hyperemic events using Multi-Modal Techniques: Spatial Frequency Domain Imaging (SFDI), transcutaneous oxygen measurement (TCOM), Pulse Oximeter, and Apple Watch.

Principal Investigator:

[name]. Assistant Professor, Indiana Center for Regenerative Medicine and Engineering at Indiana University Department of Surgery, Division of Plastic Surgery School of Medicine, Indiana University Analysis will be performed based on search of answers for the questions designed.

Q1: What are the correlations between the measurements we've taken? Are those correlations significant?

The repeated measures correlations for the measurements. Use repeated measures correlation because we have repeated measures for our data (we get values for each measurement four separate times).

Q2: What are the differences between males' and females' measurements, over time?

We have 20 subjects (13 male, 7 female). We have 5 parameters for each subject: StO2, HbO2, HbR, HbT1, and HBT2. Each measurement will be recorded at 4 time points: baseline, occlusion, reactive hyperemia, and recovery. Plots showing how subjects' measurements changed over time will be obtained. The mean measurement value for males and females, over time will be obtained. Hypothesized that males' and females' measurements follow similar patterns over time. StO2 for males will have higher average HbO2, HbR, HbT1 and HbT2 measurements than females, over all time points compared to females.

Q3. Is this male/female gap in measurements statistically significant, though?

To answer this, I fit multivariate linear regression models at each time point. Results of multivariate linear regression models, for each time point will be obtained. Multivariate models are basically just regression models with multiple outcome variables; in this case, the outcomes are the 5 measurements. The regression coefficients for the intercepts are basically the estimated average measurement for males, for that measurement, at that time point; the p values for the intercepts don't really matter. The regression coefficients for female is just the estimated average difference between males and females, for that measurement, at that time point.

Example:

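### Every outcome the SAP names is an SFDI output, so the secondary objective of comparing devices with the pulse oximeter has no stated between-device analysis

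*SAP*

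**What the plan says.** The protocol sets out a comparison of devices. Its background states that "we sought to assess the accuracy, reliability and usability of these oximeters and compare outcomes". Section 1.2, the secondary objective, reads "To compare other modalities with FDA approved Pulse Oximetry". Section 2.2, the secondary outcome, reads "Comparison of the devices provides the standard for clinical use". Section 5.0 makes the data paired by design: "Each subject will use all four devices". The exploratory objective in 1.3 is "To investigate skin color biasness in the optical Oximeters", with skin type graded on the Fitzpatrick chart.

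The analysis text is narrower. Protocol 9.0 offers a mean and a standard error for each device, from five sets of data. The SAP states: "We have 5 parameters for each subject: StO2, HbO2, HbR, HbT1, and HBT2". It then asks three kinds of question:

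- repeated-measures correlations among the measurements (Q1);
- male versus female differences (Q2 and Q3);
- skin types II and III versus IV (a second item numbered Q2).

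The regression outcomes are the same five parameters. The SAP already reports estimates, intervals and conclusions for these questions.

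**The concern.** The study was set up to compare four devices on the same people, but the SAP appears to analyse the output of one. Followed as written, the two documents would yield device means side by side. There would be no within-subject difference from the oximeter with an interval, and no measure of how far two devices disagree in one person. The skin-type question has the same limit. Without the contrast on the Innovo and Apple Watch readings, a reader cannot tell whether the reported type IV difference in StO2 is specific to SFDI or shared by the optical devices.

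**Working it through.** **1. Match outcomes to devices** (Protocol 6.0 against the SAP).

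| Device | Quantity | Named as SAP outcome | Stated contrast with the oximeter |
|---|---|---|---|
| SFDI | StO2, HbO2, HbR, HbT1, HbT2 | all five | none |
| Innovo oximeter | SpO2 | no | (reference) |
| Apple Watch | blood oxygen, % | no | none |
| TCOM | TcpO2 | no | none |

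The SFDI row rests on the protocol's text that "different regions of interest (ROI) will be taken to measure the oxygen parameters such as tissue oxygen saturation", followed by the other four names. The oximeter and watch appear in the SAP only in its title; TCOM appears there and in the abbreviation list. Protocol 6.0 once attaches the label StO2 to the oximeter, but the same paragraph says the device will measure SpO2. The SAP defines StO2 as tissue oxygen saturation, so its StO2 is the SFDI value. Result: 5 of 5 outcomes are SFDI outputs, no paired device comparison is stated, and 1 of 3 optical devices has a stated skin-type contrast.

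**2. Reproduce the SAP's worked examples** (t distribution, 20 − 2 = 18 df, t = 2.101).

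- Sex, StO2 at time 1: difference 4, CI −11 to 19. SE = 15/2.101 = 7.14; 4/7.14 = 0.56; p = 0.582 (stated 0.581).
- Skin type, StO2 at time 1: difference −20, CI −33 to −7. SE = 13/2.101 = 6.19; −20/6.19 = −3.23; p = 0.0046 (stated 0.004; 0.0029 to 0.0071 allowing for rounded inputs).

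Both agree within rounding. Both are between-subject contrasts on one SFDI parameter; neither compares devices.

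**3. Precision of a paired comparison at n = 20, one pair per subject** (unit: SD of the paired differences; t on 19 df = 2.093).

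- Bias: t/√n = 2.093/√20 = 0.47.
- Each limit of agreement: t·√(1/n + 1.96²/(2(n−1))) = 2.093·√(0.0500 + 0.1011) = 0.81.

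The documents give no SD of differences. If it were 1 or 2 saturation points (assumption), the half-widths would be 0.47 or 0.94 points for bias and 0.81 or 1.63 for each limit.

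**4. What means per device can give** (unit: SD of one device's readings, assumed equal across devices). Treating devices as unpaired, the half-width is t(38)·√(2/20) = 0.64. Pairing gives t(19)·√(2(1−r)/20) = 0.66, 0.47 or 0.21 for between-device correlation r = 0, 0.5 or 0.9. Pairing therefore helps only if r is appreciable. Limits of agreement cannot be obtained from separate means and SEs at all.

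**5. Precision of the skin-type contrast.** The split is not stated, but the SAP's intervals constrain it. In a two-group model with pooled variance, (half-width of difference / half-width of intercept)² = 1 + n₁/n₂, where n₁ is types II+III and n₂ is type IV. The half-widths are 13 and 7.5 (intercept CI 63 to 78). Allowing for rounding, n₁/n₂ runs from (12.5/8)² − 1 = 1.44 to (13.5/7)² − 1 = 2.72. Of 20 subjects, only 12/8 (1.50), 13/7 (1.86) and 14/6 (2.33) fit; 11/9 (1.22) and 15/5 (3.00) do not. The contrast half-width, 2.101·√(1/n₁ + 1/n₂), is then 0.96, 0.99 (0.985) and 1.03 (1.025) between-subject SD.

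A caution: the same formula on the sex example (half-widths 15 and 8) gives at least (14.5/8.5)² − 1 = 1.91, just above the stated 13/7 = 1.86. The inferred skin-type split is therefore a guide, not a recovered count.

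**The case against.** Much can be said for the plan. The objective and the outcome say only to compare, and name no metric; limits of agreement are this review's proposal. A reader might infer that the protocol requires a paired agreement analysis for every device, but it does not. SFDI StO2 is a tissue saturation and TcpO2 a skin oxygen level, so only the Apple Watch shares a scale with the oximeter.

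A reader might also infer that Q1 excludes the other devices. Its wording sets no device limit, and repeated-measures correlation across devices would be a within-subject analysis. The SAP's closing statement speaks only of the five measurements, which makes an SFDI-only scope likely but not certain. Even with all devices included, correlation would not measure bias or agreement.

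On skin type, the tertiary outcome in section 2.3 concerns tissue oxygenation, which the StO2 models do address. So it would be too strong to say that the exploratory aim is unanswered; its objective and its outcome measure do not match.

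Finally, nothing shows that the other readings were omitted or discarded: sections 5.0 and 10.0 plan to obtain and record them. What stands is that neither document states how they will be compared.

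**Conclusion.** The concern holds as a gap in the stated analysis. The secondary objective has no between-device estimate beyond means and standard errors per device, and the skin-type models name outcomes from one of three optical devices. It should be fixed and is cheap to fix. A reader might take it as a defect that undermines the study; that goes too far, because it touches a secondary and an exploratory objective and any repair is now post hoc.

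The bias and limit half-widths in step 3 assume 20 complete pairs and roughly normal differences. The skin-type range of 0.96 to 1.03 SD assumes that all 20 subjects fall in the two groups, pooled variance, and the split inferred from the SAP's rounded intervals.

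**What to change.** In the SAP:

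1. Add the within-subject Apple Watch minus Innovo SpO2 difference at baseline: mean bias, 95% limits of agreement, and CIs for both. State which oximeter finger (protocol 6.0 uses thumb and index) and which of the five sets in protocol 9.0 form the pair. If the sets are replicates, use them to report repeatability for each device, since the background names reliability. Report missing readings by device and phase.
2. For SFDI StO2 and TcpO2, report within-subject change by phase and make no accuracy claim against SpO2. Any between-device repeated-measures correlation is descriptive only, because all devices share the cuff-driven changes. First reconcile the protocol's three phases with the SAP's four time points.
3. Run the skin-type contrast on the Innovo and Apple Watch readings too, as exploratory estimates with CIs, and reconcile protocol 1.3 with 2.3.
4. List the variables in Q1.
5. Label these analyses as added after results were seen.

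The cost is SAP text and analysis of readings already planned; no new visit or measurement. The limits are real:

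- **Narrow range.** By the protocol's own account most healthy people read 95 to 100%, so baseline agreement says little about lower saturations. Two unrelated integer readings spread evenly over that range would differ with SD √(2·35/12) = 2.4, giving limits of only about ±4.7.
- **Small gain from pairing.** Low between-subject spread may leave little correlation to exploit.
- **Occlusion data.** Pairs may be missing or unusable. The watch goes on the wrist the subject prefers, and for TCOM "Recording will be started and waited for the oxygen level to stabilize and a fixed value will be recorded", while occlusion lasts 2 minutes. The across-phase part may shrink to baseline.

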  - b) Occlusion of the blood flow using pressure cuff at 200mmHg for 2 minutes and then collect the data during occlusion. There is a minimal risk of pain on the arm inflation of the pressure cuff up to 200mmHg. Please see literature (1) where they have used 240mmHg.
  - c) Releasing the cuff and collecting the data during the hyperemic phase (post-deflation of the cuff).

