## 9.0 Statistical Considerations

Five sets of data will be collected from each of the devices and statistical mean and standard error of deviation from the mean will calculated.

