## 12.0 Follow-up and Record Retention

The duration of the data collection will be 1-2 hours and the study will be within 6 months. The duration of record retention will be for 5 years and after that destruction or the possibility of indefinite archiving of information.

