For StO2 at time 1, it's estimated that males have an StO2 value of 62, with a 95% confidence interval of 54 to 70. It's estimated that females have StO2 values at time 1 that are 4 higher than males, on average [95% confidence interval ranges from 11 lower than males, to 19 higher than males]. That confidence interval [-11 to 19] contains 0, so there's a strong enough possibility that the difference between male and female StO2 values at time 1 is 0 (i.e. there's no difference). Because of that, the p value for Time 1/StO2/Female is 0.581, which is greater than .05, which

means we can't reject the idea the females and males have the same StO2 values at time 1.

Q2: Instead of gender, what about differences between skin type (II and III vs. IV)?

Plot of measurements over time for subjects with skin type II and III vs. skin type IV will be analyzed. The data represent the mean measurement value for skin types 2 and 3 vs skin type 4, over time. Based on the above plots, it appears that (on average) those with skin type 4 have lower StO2 and HbO2 over time, compared to those with skin type 2 and 3. Skin type 4s appear to have higher HbR and HbT1 over time, compared to skin type II and III. There's a lot of variation in HBT2 over time, and both skin type groups have similar mean values over time. Like for gender, I fit separate multivariate linear regression models for each time point. The regression coefficients for the intercepts are basically the estimated average measurement for the skin type II + III group, for that measurement, at that time point; the p values for the intercepts don't really matter. The regression coefficients for skin type IV is just the estimated average difference between 4s and 2s + 3s, for that measurement, at that time point.

Example:

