For StO2 at time 1, it's estimated that type 2s and 3s have an StO2 value of 71, with a 95% confidence interval of 63 to 78. It's estimated that type 4s have StO2 values at time 1 that are 20 lower than type 2s and 3s, on average [95% confidence interval ranges from 33 lower than 2s and 3s, to 7 lower than 2s and 3s]. That confidence interval [-33 to -7] does not contain 0, meaning we're confident that the difference between 4s and 2s/3s is not 0. Because of that, the p value for Time 1/StO2/Female is 0.004, which is less than .05, which means we can reject the idea that 4s and 2s/3s have the same StO2 values at time 1. Most of the 5 measurements are correlated with one another. Females and males had similar measurements at baseline, but started to differ in HbO2, HbR, HbT1, and HbT2 from inflation onwards. Those with skin type 4 had lower StO2, higher HbR, and higher HbT1 compared to those with skin type 2 and 3, at all-time points; the two groups didn't significantly differ in regard to HbO2 and HbT2 at any time.

Abbreviation StO2= tissue oxygen saturation HbO2=oxy hemoglobin HbR= deoxy hemoglobin HbT1= superficial perfusion hemoglobin HbT2= deep perfusion hemoglobin TCOM=trans-cutaneous oxygen measurement

SFDI=spatial frequency domain imaging

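### The SAP analyses a recovery reading that Protocol Section 6.0 neither lists nor times; separately, nothing ties the watch to the cuffed arm in the device comparison

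*SAP*

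**What the plan says.** **Time points.** The SAP (under its first question 2, on sex) says: "Each measurement will be recorded at 4 time points: baseline, occlusion, reactive hyperemia, and recovery". Question 1 of the SAP also counts four values per measurement. Question 3 fits a separate multivariate regression at each time point, with five SFDI parameters as outcomes, and the skin-type section repeats this.

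Protocol Section 6.0, step 4, orders the collection as (a) baseline, (b) during a two-minute cuff occlusion, and (c) "Releasing the cuff and collecting the data during the hyperemic phase (post-deflation of the cuff". Step (c) is the last one. No step gives a time after release.

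Three other statements touch on the schedule:
- The study title, as printed in the SAP, refers to measurement "before, during and after hyperemic events".
- Protocol Section 9.0 says: "Five sets of data will be collected from each of the devices".
- Protocol Section 12.0 says: "The duration of the data collection will be 1-2 hours".

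**Placement.** Section 6.0 puts the watch on the wrist that the user prefers. Step 4b inflates a cuff on the arm without naming a side. The side of the imaged hand and of the finger sensors is not given either. The Background says subjects will be measured at the same site. Section 1.2 makes comparison with the pulse oximeter the secondary objective.

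**The concern.** The two documents disagree on how many times each subject is measured. A team that followed step 4 of Section 6.0 and nothing else could finish the visit without a recovery reading, yet the SAP gives recovery a model of its own for each grouping. Because the hyperemic reading has no time after release either, nothing marks where reactive hyperemia ends and recovery begins. Two subjects' readings could carry the same label at different points of the same physiological curve, or different labels at the same point.

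The watch raises a separate issue. Step 4 uses all the devices at each phase, including those in which the cuff changes flow in one arm. If the preferred wrist is on the other arm, the watch samples a limb with normal flow while the finger sensor may sample the cuffed one. A difference between limbs could then be read as a difference between the watch and the pulse oximeter.

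**Working it through.** **1. Count the time points.**

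| Phase | SAP | Protocol 6.0, step 4 | Time after release given |
|---|---|---|---|
| Baseline | yes | yes (a) | not applicable |
| Occlusion | yes | yes (b) | not applicable |
| Reactive hyperemia | yes | yes (c) | none |
| Recovery | yes | not listed | none |

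The SAP's figure is 4. The count from Section 6.0 is 3. The difference is recovery.

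**2. See whether another passage supplies the missing step.**
- The title's wording on the period after hyperemia signals a later reading but attaches no step or time to it.
- The five data sets in Section 9.0 match neither 3 nor 4 phases, and the text does not say whether they are phases, repeats or something else.
- The session length of 1 to 2 hours bounds the visit. It does not place a recovery reading within it, and of a single SFDI scan the protocol says: "Actual scanning takes less than 60 seconds".

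**3. What recovery carries in the SAP.** Inputs from the SAP: 20 subjects, 5 parameters, 4 time points, 2 groupings (sex, skin type).
- Models per grouping: 1 of 4 is at recovery.
- Group coefficients per grouping: 5 × 4 = 20, of which 5 × 1 = 5 are at recovery.
- Over both groupings: 2 × 20 = 40, of which 2 × 5 = 10 are at recovery.
- Repeated-measures correlation (question 1): observations per parameter are 20 × 4 = 80 with recovery and 20 × 3 = 60 without. Degrees of freedom, N(k − 1) − 1, are 20 × 3 − 1 = 59 with it and 20 × 2 − 1 = 39 without.

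**4. What the reported conclusions draw on.** The SAP already states that subjects with skin type 4 "had lower StO2, higher HbR, and higher HbT1 compared to those with skin type 2 and 3, at all-time points". That is 3 parameters × 4 time points = 12 differences, of which 3 are at recovery and 9 are at phases that Section 6.0 does list. The sex summary says that four parameters diverged once the cuff was inflated and afterwards. Read naturally, this also reaches recovery, but results are not itemised by time point.

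**5. Watch and cuff.** Section 5.0 has every subject use all four devices, and step 4 applies the devices at each phase. The watch rule goes by preference, the cuff's side is unstated, and no sentence links them. Baseline is unaffected, because the cuff has not yet been inflated. Occlusion and hyperemia are exposed. The documents do not record how often watch and cuff were on opposite arms, so no count can be derived. The SAP's regressions contain only SFDI outcomes, so this part does not touch them.

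**The case against.** The best reply on timing is that recovery was plainly intended. The SAP names it, the title points to it, and step 4c does not say that only one reading may be taken after release. The contents list also names a Study Schema that is not in the text available here, and it may show the fourth reading. This stands as a limit on the claim: the gap is in Section 6.0, and one should not infer that the protocol as a whole omits recovery or that the readings were not taken.

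It is also fair to say that step 4c does restrict its reading to the hyperemic phase. A reader might infer that the session length is the only bound on post-release readings. That goes too far for the hyperemic reading, although the bound has no minutes attached.

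On placement, the reply is that side is unstated for every device, so the gap is general, and that the Background's same-site statement shows the intent. The first is true and is why the fix covers all sensors; the watch differs only in having a stated rule that can lead away from the cuffed arm. The second does not fix a side.

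Finally, skin type is a tertiary objective, sex is not a stated objective, and results for 20 subjects already exist. This lowers the stakes and means that for these data the remedy is mainly disclosure. It does not remove the conflict between the documents.

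**Conclusion.** Both parts hold, as points that should be corrected; neither shows a reported result to be wrong.

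**Recovery.** SAP and Section 6.0 conflict by one time point, which carries a quarter of the group coefficients (10 of 40). Varying times after release would mainly add noise to the sex and skin-type contrasts and make the two post-release phases harder to tell apart. Three stronger readings are tempting and unsupported:
- That the contrasts are biased. Nothing links reading time to sex or skin type.
- That precision falls by a stated amount. The documents give no spread of reading times, so any figure would come from the assumption put in.
- That the skin-type conclusion depends on recovery. Only 3 of its 12 differences lie there.

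**Watch.** The placement rule permits limb and device to be confounded at occlusion and hyperemia, in the comparison named as the secondary objective. A reader might infer that most watch readings are spoiled. The documents do not show that even one is.

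The conclusions assume that the visible Section 6.0 is the operative schedule and that all four devices are read at each phase, as step 4 implies.

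**What to change.** **Recovery**
- Reconcile the passages: list the recovery reading in Section 6.0, set a fixed time after cuff release for each of the two post-release readings, and say how the five data sets per device map to phases. The times themselves are for the study team to choose.
- For completed visits, report the actual times after release, or state that they were not recorded.
- Keep recovery in the SAP. Results have been seen, and dropping a time point now would invite a charge of selective reporting.

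**Placement**
- Put the watch, the imaged hand and the finger sensors on the cuffed arm. Record which arm it was, and record a failed reading as failed.
- For completed visits, report the device comparison both with and without watch readings known to come from the opposite arm. Where the arm is unknown, state this as a limitation.

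**Cost.** A short wording change in Section 6.0 and the SAP, and three data-sheet fields (arm, time after release, failed reading). Some subjects will wear the watch on the less-preferred wrist, and some same-arm watch readings during occlusion may fail. For the 20 subjects already reported, only the reporting steps still apply.

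### The SAP hypothesises a male/female gap across all phases, but tests it only phase by phase, with no contrast across phases, no sex-by-phase term and no decision rule

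*SAP*

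**What the plan says.** SAP Q2 sets out the data: "We have 20 subjects (13 male, 7 female"), five SFDI parameters, and four phases ("Each measurement will be recorded at 4 time points: baseline, occlusion, reactive hyperemia, and recovery"). It then makes two statements about sex. The first concerns shape: "Hypothesized that males' and females' measurements follow similar patterns over time". The second concerns level: males "will have higher average HbO2, HbR, HbT1 and HbT2 measurements than females, over all time points compared to females". Plots and group means over time are planned, with no test attached to them.

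Q3 asks whether this gap is significant. The answer is: "To answer this, I fit multivariate linear regression models at each time point", and "Results of multivariate linear regression models, for each time point will be obtained". Each sex coefficient is defined as a difference for one measurement at one time point.

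The closing summary, after the skin-type example, reports that the sexes were alike at baseline but "started to differ in HbO2, HbR, HbT1, and HbT2 from inflation onwards". It does not say which sex was higher or whether the hypothesis was borne out.

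The protocol does not fill the gap. Its Statistical Considerations (section 9.0) plan only means and a measure of their error, and its objectives and outcome measures (sections 1.1 to 1.3 and 2.1 to 2.3) do not mention sex.

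**The concern.** Each parameter has one hypothesis about level across the phases and gets four separate answers. Without a stated rule, the verdict can be chosen once the four p values are known: supported because three phases differ, or refuted because baseline does not. The SAP's own closing summary has this mixed pattern.

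The hypothesis of similar patterns is a statement about the sex-by-phase interaction. Four regressions fitted separately cannot test it. A significant result at one phase and a non-significant result at another is not evidence that the gap differs between them.

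The SAP does recognise that the readings are repeated within subject, but uses this only for the Q1 correlations.

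**Working it through.** **1. Reproducing the SAP's worked figure.** Inputs from the Q3 example (StO2, time 1): difference 4, 95% CI -11 to 19, p = 0.581. Regression on sex at one phase is a pooled two-sample t test with 13 + 7 - 2 = 18 df and critical value 2.101.
- SE = 15 / 2.101 = 7.14
- t = 4 / 7.14 = 0.560, two-sided p = 0.582

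This agrees with 0.581; rounding of the inputs allows 0.536 to 0.630. So the planned test is a single-phase comparison, as described. One side note: with 13 and 7 subjects the half-width of the difference should be sqrt(1 + 13/7) = 1.69 times that of the male mean. The stated 54 to 70 has half-width 8, at most 8.5 before rounding, which gives at most 14.4. The stated half-width is 15, at least 14.5. The example may therefore not rest on complete data with a 13/7 split.

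**2. Number of tests.** Named parameters: 4 × 4 phases = 16. With StO2: 5 × 4 = 20. If all were independent, the chance of at least one false positive would be 1 - 0.95^4 = 18.5% for one parameter, 1 - 0.95^16 = 56.0% for 16 tests and 1 - 0.95^20 = 64.2% for 20. These are upper-end illustrations, because the readings are correlated.

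**3. How much the missing rule matters.** The documents give no correlation between phases and no SD for a named parameter, so both the correlation (rho) and the effect are assumed. Simulation: 100,000 runs, 13 against 7 subjects, one parameter, four readings with equal SD and equal correlation, two-sided 0.05 tests.

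With no true gap, at least one of the four tests is significant in 19% (rho 0), 16% (rho 0.5) or 10% (rho 0.9) of studies. One test of each subject's four-phase mean gives 5%.

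Percentage of studies declaring the hypothesis supported (significant, males higher):

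| True gap | rho | Any of four | Averaged | All four |
|---|---|---|---|---|
| 1 SD at every phase | 0 | 95 | 98 | 7 |
| | 0.5 | 83 | 72 | 21 |
| | 0.9 | 66 | 56 | 39 |
| 0 at baseline, 1 SD at the other three | 0 | 89 | 86 | 0.3 |
| | 0.5 | 78 | 48 | 2 |
| | 0.9 | 64 | 35 | 3 |

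The second pattern resembles the one the SAP reports, and it separates the two readings. The pooled hypothesis is then true (average gap 0.75 SD), while the every-phase hypothesis is false.

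**4. Precision of an averaged contrast.** The variance of a mean of four such readings is s²(1 + 3·rho)/4, so the CI half-width shrinks by sqrt((1 + 3·rho)/4): 0.791, 0.880 and 0.962 at rho 0.5, 0.7 and 0.9. Applied to the 15-point StO2 half-width this gives 11.9, 13.2 and 14.4, that is 21%, 12% and 4% narrower. StO2 is not one of the four named parameters; it is used because it has the only sex-difference interval in the documents.

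**5. Dilution.** If the gap is zero at baseline and equal at the other three phases, the averaged gap is 0.75 of the phase gap. Signal-to-noise relative to one post-baseline test is 0.75/0.791 = 0.95, 0.75/0.880 = 0.85 and 0.75/0.962 = 0.78. The two break even where (1 + 3·rho)/4 = 0.75², that is at rho = 0.42. Above that, averaging is the weaker test for this pattern.

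**The case against.** The hypothesis sentence is garbled: it opens with StO2 and then lists four other parameters. Elsewhere the SAP uses average for a mean across subjects at one phase, and for skin type the closing summary uses a nearly identical time phrase to mean each phase. A reader might infer that the hypothesis is definitely about a mean pooled over time and gets no answer at all. The documents do not support that. On the every-phase reading the four regressions do estimate its components, and the baseline result bears on it directly; descriptive means over time are planned as well. What stands is that this reading needs all four phases to agree, and no such rule is given.

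A reader might also infer that averaging would give a more powerful test. That does not follow either: it loses power if the gap is absent at baseline, and the precision figures rest on an assumed correlation and on equal SD across phases that cuff occlusion may well break.

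Two further points stand. Sex is in no protocol objective, so this is an exploratory question in 20 volunteers. And because the SAP already reports results, a contrast chosen now is itself chosen after seeing data. Neither supplies the missing decision rule.

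**Conclusion.** The point holds on either reading of the sentence. The plan gives phase-specific estimates and p values, but no inferential verdict on the gap across phases and no test of similar patterns. The reported mixed result can be argued both ways.

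The size depends on assumptions. With a 1 SD gap at every phase and rho 0.5, the unstated rule moves the chance of declaring support from 21% to 83%; with no gap at baseline, from 2% to 78%. The spread between rules is the finding, not any single figure. A precision gain of about 4% to 21% (rho 0.9 to 0.5) is illustrative only and is not the main argument.

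Severity is modest: the remedy is worth making, but no protocol objective rests on it.

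**What to change.** For each parameter, replace the four separate regressions by one repeated-measures model with sex, phase, sex-by-phase and a random subject effect. In the SAP:

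- State which reading of the hypothesis is meant: pooled over phases, or males higher at every phase. If the latter, state that all four phases must agree.
- Report the sex difference averaged over the four phases, with its 95% CI, as the test of the hypothesis across phases. This is one test per parameter: 4 instead of 16, or 5 instead of 20 with StO2.
- Report the sex-by-phase term as the test of similar patterns.
- Keep the four phase-specific differences with CIs as supporting estimates.
- Label the analysis as added after data review.

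The cost is SAP wording and one model per parameter on data already held. There are three downsides to state. The averaged contrast is diluted if the gap is absent at baseline. The interaction test has low power with 13 and 7 subjects, so a non-significant result must not be read as showing similar patterns. A simple random subject effect assumes equal variance and correlation across phases, which should be checked.
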